## **2. Study Objectives**

The primary objective is to establish the safe dosing and tolerability of TIL-TC150, a CBD rich cannabis plant extract administered as an oral solution for children with severe refractory epilepsy. Dosing safety will be measured by blood work evaluation of renal, hematologic and hepatic function and of AED levels, by parent/caregiver report, by physician assessment, and by assessing caregiver reported tolerability and the Pediatric Epilepsy Side Effects Questionnaire (PESQ).

As secondary measures we will also assess:

1. The impact of therapy on quality of life using the Quality of Life in Childhood Epilepsy (QOLCE) questionnaire and on everyday behaviours using the Vineland Adaptive Behavior Scales, Second Edition.

2. Change in seizure frequency from baseline using the following measures:

Parent-reported seizure diary

24 hour Ambulatory EEG study (measurements: (a) percentage change in electrographic seizure frequency and (b) using spike detection software we will measure the percentage change in interictal activity during the recording)

Number of episodes of Status Epilepticus – defined as convulsive seizure lasting longer than 10 minutes

Frequency of use of rescue medications (Lorazepam, Midazolam, or Diazepam).

Number of visits to emergency department / hospitalizations with seizures

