### 3.4 Primary Study Endpoint

The primary endpoint is establishing the maximal safely tolerated dose of TIL-TC150 in our study population.

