### 5.2 Treatment Regimen

Each participant will start the treatment with a dose of 2mg/kg/day CBD given in two equal doses each day. The first dose will be given during the Baseline (Week 0) visit. Following this dose the participant will be observed by study personnel for a period of 2 hours. The participant's parent/legal guardian will increase the participant's dose by 2mg/kg/day CBD every 7 days as tolerated, to a maximal dose of 16mg/kg/day CBD. Once optimal dose is determined for each participant they may continue the treatment for the duration of study follow-up and thereafter it will be continued if wished by participants.

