After this time point participants will resume care with their regular pediatric neurologist. Written communication regarding their therapy and current dosing will be forwarded by the study investigators to this physician. In addition, the study team will be available by telephone or email to provide support to physicians as participants' transition back to their care; in particular should they have any questions about TIL-TC150.

For the weeks of the study that the participants are not being evaluated in person at The Hospital for Sick Children, follow-up emails and/or phone calls will be made. This communication will occur in between the clinical visits for the intervention period - week 1, 3, 5, 6, 7, 10, 14, and 18. Participant's parent/ legal guardian will be asked about their child's dosage to ensure correct titration or if already at maximal study protocol dose (as determined during the intervention period) how they are tolerating it. Adverse events and concomitant medications will always be assessed and any concerns participant, parent/caregiver may have will be addressed.

The study participant will be given a window of +/- 3 days around the timing of each study visit during the intervention period and +/- 14 days for the post-intervention longitudinal visit scheduling.

5.8 Schedule of Events table:

| Study Period             | Week # | Participant/ study team interaction   | TIL-TC150Dose   |
|---------------------------------|---------------|--|--|
| Pre- Intervention Period | -4            | Clinic visit – education, baseline physical and neurological review and urine test for THC for those only who have not been on cannabinoids for at least last 60 days.                                       | None   |
| Baseline analysis        | -4 to 0       | Participant parent/legal guardian completion of seizure diary; 24 hour ambulatory EEG, psychologist will arrange for parent/caregiver to complete a Vineland assessment                                      | None   |
| Intervention period      | 0             | Clinic visit – education, weight, physical and neurological review; baseline bloodwork; collection of baseline seizure diary; education regarding dosing of study product; parent to complete baseline QOLCE | Starting at 2mg/kg/day CBD divided in 2 equal doses; first dose given in clinic with 2 hours of observation post-dose. |

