|                                 | 1             | Telephone and/ or email contact by study team to determine dosing and tolerability   | Once tolerance ensured, increase dose to 4mg/kg/day CBD divided twice daily  |

|    |  |   |
|----|--|---|
| 2  | Clinic visit – tolerance review, adverse events,; physical and neurological exam; parent/legal guardian to complete PESQ; seizure diary review   | Once tolerance ensured, increase to 6mg/kg/day CBD divided twice daily  |
| 3  | Telephone and/ or email contact by study team to determine dosing and tolerability   | Once tolerance ensured, increase to 8mg/kg/day CBD divided twice daily  |
| 4  | Clinic visit – tolerance review, adverse events; physical and neurological exam; parent/legal guardian to complete PESQ; seizure diary review; bloodwork   | Once tolerance ensured, increase to 10mg/kg/day CBD divided twice daily |
| 5  | Telephone and/ or email contact by study team to determine dosing and tolerability   | Once tolerance ensured, increase to 12mg/kg/day CBD divided twice daily |
| 6  | Telephone and/ or email contact by study team to determine dosing and tolerability   | Once tolerance ensured, increase to 14mg/kg/day CBD divided twice daily |
| 7  | Telephone and/ or email contact by study team to determine dosing and tolerability   | Once tolerance ensured, increase to 16mg/kg/day CBD divided twice daily |
| 8  | Clinic visit – tolerance review, adverse events; physical and neurological exam; parent/legal guardian to complete PESQ and QOLCE; seizure diary review; bloodwork performed once child is at target / maximal tolerated dose (any stage from week 8-16) | If tolerated, dose to continue at 16mg/kg/day CBD divided twice daily   |
| 10 | Telephone and/ or email contact by study team to determine dosing and tolerability   | If tolerated, dose to continue at 16mg/kg/day CBD divided twice daily   |
| 12 | Clinic visit – tolerance review, adverse events; physical and neurological exam; parent/legal guardian to complete PESQ; seizure diary review; bloodwork performed once at target / maximal tolerated dose (if not done previously)                      | If tolerated, dose to continue at 16mg/kg/day CBD divided twice daily   |
| 14 | Telephone and/ or email contact by study team to determine dosing and tolerability   | If tolerated, dose to continue at 16mg/kg/day CBD divided twice daily   |

|                                      |       |  |   |
|--------------------------------------|-------|--|---|

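### During escalation the PESQ falls on only 3 of 8 dose levels and none is triggered by a hold or reduction, so standardised side-effect scores may favour the doses children kept

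*Combined protocol and SAP*

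**What the plan says.** Section 3.4 states: "The primary endpoint is establishing the maximal safely tolerated dose of TIL-TC150 in our study population". Section 2 says that dosing safety will be judged partly "by assessing caregiver reported tolerability and the Pediatric Epilepsy Side Effects Questionnaire (PESQ"), alongside bloodwork, parent report and physician assessment.

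Section 5.2 sets the titration: "Each participant will start the treatment with a dose of 2mg/kg/day CBD given in two equal doses each day", and the parent is then to "increase the participant's dose by 2mg/kg/day CBD every 7 days as tolerated, to a maximal dose of 16mg/kg/day CBD". The table in section 5.8 assigns one increase to each of Weeks 1 to 7, starting with "Once tolerance ensured, increase dose to 4mg/kg/day CBD divided twice daily" at Week 1 and "Once tolerance ensured, increase to 6mg/kg/day CBD divided twice daily" at Week 2. The Week 5 entry, a telephone or email contact, reads "Once tolerance ensured, increase to 12mg/kg/day CBD divided twice daily".

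Section 7.2 ties the PESQ to clinic visits. Sections 5.6 and 5.8 list it at Weeks 2, 4, 8, 12 and 16 of the intervention period. Between visits there are telephone or email contacts at "week 1, 3, 5, 6, 7, 10, 14, and 18" (end of section 5.7). Dose, tolerability, adverse events and concomitant medication are covered there, but no PESQ is listed. The only PESQ outside the visit calendar is at the clinic visit offered after withdrawal (section 4.4.2).

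**The concern.** The study is meant to find the highest dose each child tolerates. The most informative moment for a tolerability instrument is the dose at which a child gets into difficulty. The PESQ is the only side-effect questionnaire named under the primary objective, and its calendar follows clinic visits rather than dose levels. Visits become sparser just as the dose passes 8 mg/kg/day: four increases (to 10, 12, 14 and 16) occur from the Week 4 visit up to the Week 8 visit, with no PESQ, scheduled examination or scheduled bloodwork in between.

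If a child struggles on one of those doses and is reduced before Week 8, the next form describes the dose the child was moved to. Summaries of PESQ scores could then read more favourably than the escalation was. The Study Summary also promises frequency and severity of adverse events by dosage, while section 7 gives no severity grading scale, so a standardised score at each dose would be useful.

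**Working it through.** **Inputs.** Start 2 mg/kg/day, step 2, interval 7 days, maximum 16 (section 5.2). This gives 8 levels and (16 − 2)/2 = 7 increases. Contact types and PESQ visits are from sections 5.6 to 5.8 and 7.2.

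**Reproducing the plan's schedule.** Dose after the step at Week w = min(16, 2 + 2w). At Week 7: 2 + 2 × 7 = 16, as in the table.

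**Dose a child arrives on** = min(16, 2 + 2(w − 1)):

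| Week | Contact | Dose on arrival (mg/kg/day) | PESQ |
|---|---|---|---|
| 1 | phone/email | 2 | no |
| 2 | clinic | 4 | yes |
| 3 | phone/email | 6 | no |
| 4 | clinic | 8 | yes |
| 5 | phone/email | 10 | no |
| 6 | phone/email | 12 | no |
| 7 | phone/email | 14 | no |
| 8 | clinic | 16 | yes |

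The PESQs at Weeks 12 and 16 again fall on 16. Coverage is 3 of 8 levels (37.5%); 2, 6, 10, 12 and 14 are unscored.

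**A child who is reduced.** The documents say only that dose or frequency may be adjusted (section 1.7.1). For illustration, assume a reduction of one level before Week 8, after which the dose is held.

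| Level not tolerated | Started at Week | Weeks to next PESQ | PESQ doses at Weeks 2, 4, 8 |
|---|---|---|---|
| 10 | 4 | 8 − 4 = 4 | 4, 8, 8 |
| 12 | 5 | 8 − 5 = 3 | 4, 8, 10 |
| 14 | 6 | 8 − 6 = 2 | 4, 8, 12 |

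The level that was not tolerated is scored in none of the three. Scores on 4 and 8 from before the failure do exist.

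**Sensitivity.**
- Visits 1 to 3 days late (within the window), with parents still stepping up every 7 days: scored levels become 6, 10 and 16, still 3 of 8. A failed 10 could then be scored. Early visits leave 4, 8 and 16.
- One week's delay anywhere: 4 levels are scored, including 14 at Week 8 and 16 at Week 12. Levels 10 and 12 are unscored wherever the delay falls.
- Section 3.2 and the Week 8 text of section 5.6 place an increase at Week 8, whereas the table reaches 16 at Week 7. Read literally, this is the one-week-delay case: 4 of 8, with 10 and 12 unscored.
- Section 7.2 could be read as adding a PESQ at Week 0, which sections 5.6 and 5.8 do not list. That would be a baseline or first-dose score, so the count stands.

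**The case against.** The strongest reply is that tolerability by dose is already collected. Adverse events are assessed at every contact (section 5.7), by direct questioning (section 7.2), and entered on a dedicated case report form (section 7.3). The by-dosage reporting in the Study Summary concerns adverse events, not PESQ scores. The study team determines the maximally tolerated dose (section 5.6), and nowhere is the PESQ the criterion. Once a child settles on a dose, including 10, 12 or 14, the later visits score it. After withdrawal, the dose reached and a PESQ are documented, though that visit may come weeks later. All of this stands, and it confines the point to standardised scoring.

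A reader might infer that the PESQ gap undermines the primary endpoint, or that intolerance at 10 to 14 goes unrecorded. The provisions above rule out both.

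A reader might also want a percentage. Levels 6, 10, 12 and 14 are 4 of the 7 escalated levels (57%), and 10, 12 and 14 are 3 of the 4 levels from 10 to 16 (75%). Neither figure is supportable as a rate of missed events. Both need intolerance to be equally likely at each level, which the documents do not say, and both need the child to stay on the poorly tolerated dose until the next contact. Section 1.5 reports diarrhea and weight loss above 15 mg/kg/day in an earlier open-label study. If intolerance occurs only at 16 and the child is still on it at Week 8, none is missed. If every child is reduced before the next visit, all are missed, including failures at 4, 8 and 16.

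Finally, the reduction itself is an assumption: a child still on the poorly tolerated dose at Week 8 would be scored on it. The recall period of the PESQ is not given either. If it spans several weeks, the Week 8 form may pick up symptoms from 10 to 14 but cannot assign them to a dose.

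**Conclusion.** The point holds in a limited form. On the table's schedule the PESQ covers 3 of 8 levels during escalation (4 of 8 if the Week 8 increase is taken literally), and no PESQ is tied to a hold or reduction. A child reduced from 10, 12 or 14 before Week 8 has, after the failure, PESQ scores only on the reduced dose. PESQ summaries may therefore favour retained doses. The direction is plausible, but its size cannot be calculated: the share of intolerance events without a PESQ at the offending dose could be anything from 0 to 100%, depending on where intolerance occurs and how soon the dose is reduced.

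This rests on the section 5.8 table, on escalation without delay, and on a reduction before Week 8. What is lost is standardised scoring by dose. Adverse-event recording and the determination of the tolerated dose are unaffected. This is a worthwhile low-cost improvement rather than a flaw in the primary endpoint.

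**What to change.** - Have the parent complete a PESQ, by email or telephone, whenever a dose is held, reduced or stopped, referring to the dose in force before the change. This matters most, because weekly forms alone can miss a reduction made between contacts.
- Add the PESQ at the existing Week 1, 3, 5, 6 and 7 contacts, before any dose change. This adds levels 2, 6, 10, 12 and 14 and takes an on-schedule child from 3 of 8 to 8 of 8.
- Record the mg/kg/day in force on every PESQ form in REDCap, and state the recall period.
- Report PESQ at the highest dose tried as well as at the dose retained.
- Reconcile section 3.2 and the Week 8 text of section 5.6 with the table in section 5.8 on when the last increase occurs.

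The cost is about five more short forms per child, plus one per dose change, and a little staff time at contacts already scheduled. No visit, procedure or dosing rule is added. The documents do not show whether the form suits telephone use or weekly repetition, so the team should check that first. If it does not, the form at each hold, reduction or stop is the part to keep.

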## **6. Assessment of Efficacy**

### 6.1 Specification of Efficacy Parameters

This is a phase 1 dosing and tolerability study. Efficacy of CBD is not a primary outcome. However, as a secondary outcome we will report change in seizure frequency, severity by parent/caregiver reporting and change in EEG by objective prolonged 24 hour recording prior to and at maximal dose of intervention.

### 6.2 Methods of Assessing

Seizure frequency is measured by parent/caregiver in a daily diary. This will be reviewed at each clinic visit and during each phone call/email to track change and ensure compliance with reporting. Seizure severity will be measured by frequency of

rescue medication administration, frequency of status epilepticus and frequency of ER attendance /hospitalization, recorded in a daily diary. In addition to this baseline analysis of EEG will be performed for each participant using an ambulatory EEG recording for 24 hours. Pre-intervention ictal and interictal EEG patterns will be compared with a post-intervention study (once maximal dose of treatment has been achieved). EEG analysis will be performed by 2 board certified electroencephalographers (part of the study team) at the end of the primary intervention period. They will report all EEG studies blinded to whether the recording is performed pre- or post therapy. They will record the number of electrographic seizures during the study and use spike detection software to provide an objective measure of the percentage of interictal activity during each study.

## **7. Assessment of Safety and Adverse Events**

### 7.1 Specification of Safety Parameters

Each participant will be carefully screened for suitability prior to commencement of the intervention. If the study team feels that any pre-existing conditions place the participant at risk they will be excluded from participation. Once enrolled in the study each participant and parent/legal guardian will receive education regarding the administration, dosing and schedule of the study treatment from the study investigator physician, study nurse and the study pharmacist. This information will be reviewed and dosing schedule re-evaluated at every clinic visit and phone call / email follow up. During each clinic visit there will be an evaluation of tolerability of the study treatment and of possible adverse events.

If at any stage during the study any adverse events are suspected they will immediately be evaluated by study team. The adverse event reporting period is from the initiation of the study treatment until the end of study treatment follow-up.

An *adverse event* is any symptom, sign, illness or experience that develops or worsens in severity during the course of the study. Intercurrent illness or injuries should be regarded as adverse events. Abnormal results of diagnostic procedures are considered

adverse events, if the abnormality leads to study withdrawal, is associated with clinical signs or symptoms, leads to additional treatment or diagnostic tests, is considered by the study team to be of clinical significance or is considered a serious adverse event.

*A serious adverse event* is one which is:

- fatal
- life-threatening
- requires hospitalization or prolongs hospital stay
- results in persistent or significant disability or incapacity
- a congenital anomaly or birth defect
- an important medical event (not immediately life-threatening but of significant clinical importance)

All adverse events that do not meet the criteria for seriousness should be considered *non-serious adverse events*.

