## Study Summary

|                                       |  |
|---------------------------------------|--|
| Title                                 | Cannabinoid Therapy in Medically Refractory Pediatric Epilepsy – Phase 1: Dosing and Tolerability Study of a Cannabidiol-Rich Whole Plant Extract of Cannabis.   |
| Short Title                           | Cannabinoid Therapy for Pediatric Epilepsy   |
| Phase                                 | 1  |
| Methodology                           | Open-label Intervention  |
| Study Duration                        | 20 weeks to primary analysis with continued follow-up until 64 weeks completed   |
| Study Center                          | The Hospital for Sick Children, Toronto Ontario  |
| Objectives                            | To determine the tolerability and optimal dose of 50:1 ratio CBD:THC Cannabis extract as an adjunct treatment in children with severe drug resistant epilepsy  |
| Number of Subjects                    | 20   |
| Diagnosis and Main Inclusion Criteria | Patients with Dravet Syndrome

Between ages of 1 and 18 years old male or female

Must have failed 2 AEDs at therapeutic doses and be on current regimen of 1-4 AEDs which have been stable doses for 4 weeks  |
| Study Product, Dose, Route, Regimen   | TIL-TC150 Oil is the study product
The active ingredients in TIL-TC150 Oil are THC and CBD, present in a 1:50 ratio. These active ingredients are derived from Cannabis sativa L. strains produced by Tilray and suspended in a grape seed oil. This suspension is administered at a dose of 2mg/kg/day CBD divided BID and titrated up to a maximal dose of 16mg/kg/day CBD (or maximal tolerated). |
| Duration of Administration            | Study period: primary safety and outcome data at 20 weeks with longer follow-up of safety and tolerability in those who chose to continue after the 20-week period and will be followed up to 64 weeks.  |
| Reference Therapy                     | None   |
| Statistical methodology               | The primary aims of this study are to determine the maximal tolerated dose of TIL-TC150 Oil Cannabis Extract in children with drug resistant epilepsies. Descriptive statistics will be used to quantify the frequency and severity of adverse events that are   |

|  |  |
|--|--|
|  | reported for the various dosages that are employed |
|--|--|

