## Figure 1. Cannabidiol Structure

CBD is highly lipid soluble and is a potent inhibitor of CYP2B6, CYP2C8, CYP2C9, CYP2C19, and CYP3A4. The effects of other concomitant drug levels metabolized by these enzyme systems are not known. CBD is excreted in the urine and faeces. The plasma peaks vary significantly between individuals but are typically between 1 to 2 hours. The CBD levels are detected up to 8 hours post administration. The adverse drug reactions of CBD that have been indicated in trials include headache, dizziness, fatigue, loss of appetite, oral numbness, dry mouth, neck pain, feeling strange, depression, lack of taste or changed taste, gastrointestinal disturbances, feeling weak, falls, shakiness, muscle stiffness, unusual dreams, nose bleeds, hot or cold flashes, and heartburn.

Cannabinoids: Increases in systolic BP over time (Sativex = 3 hrs), and decreases in diastolic BP with noted heart rate increase (Sativex = 4-8 hrs) [1] However, this is anticipated to be due to the THC content. Much of the published data refers to Sativex which contains 50% THC and many of the adverse effects are considered in keeping with the psychoactive THC effects.

Phytocannabinoids exhibit very low mammalian toxicity, and mixtures of cannabinoids are *less toxic* than pure THC. [2] Therefore, a mixture of other cannabinoids (terpenoids, etc.) may also reduce any potential toxicity issues due to having a high CBD product.

The following are the most common side effects of AEDs and/or high-THC cannabis. However, since our product is very low in THC we anticipate that these will be minor or rare:

- Dizziness, somnolence, fatigue, irritability, ataxia, blurred vision, diplopia vision, rashes, and motor incoordination / falls.
- Gastrointestinal (anorexia, loss of appetite, nausea, vomiting, and weight loss).Psychiatric and behavioural adverse reactions such as aggression, hostility, irritability, anger, and homicidal ideation / threats.

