## 1.7 Research Risks and Benefits

### 1.7.1 Risk of Study Product

Cannabinoids have not been extensively studied and therefore like with any drug, not all risks are known. The possible adverse drug reactions may include headache, dizziness, fatigue, drowsiness, somnolence, loss of appetite, oral numbness, dry mouth, neck pain, feeling strange, depression, lack of taste or changed taste, GI disturbances, feeling weak, falls, shakiness, muscle stiffness, unusual dreams, nose bleeds, hot or cold flashes, and heartburn. All patients will be closely monitored for adverse events during titration and treatment period. Dose and/or frequency may be adjusted as appropriate.

From the study recently published by Devinsky et al, [32] their prominent side effects were somnolence (25%), diarrhea (19% at least one episode however only 2% were classified as a serious adverse event of diarrhea), weight loss, weight gain, fatigue (13%). Status epilepticus was reported in 6% (9 participants) during their study, however it is difficult to ascertain whether this was related to therapy or in keeping with their inherent risk of status epilepticus due to their refractory epilepsy

Potential drug interactions may occur as CBD is a potent inhibitor of CYP2B6, CYP2C8, CYP2C9, CYP2C19, and CYP3A4. The effects of other concomitant AED and other drug levels metabolized by these enzyme systems are not fully known, but it may increase their levels leading to potential toxicities. Therefore, AED plasma levels will be measured at baseline and at day 28 following first CBD dose. AEDs may be adjusted as needed based on signs and symptoms of toxicity and/or changes in drug levels.

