#### **3.1 Pre-intervention period (4 weeks)**

This period is the first four weeks after the patient is enrolled. Once enrolled, the participant's legal guardian will be educated about maintaining a detailed seizure diary during this 4 week period to allow baseline analysis of seizure frequency. As an objective measure of seizure frequency, during this 4 week period all enrolled

participants will undergo a 24 hour ambulatory EEG study to also assess ictal and interictal epileptiform activity.

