### 5.3 Concomitant treatments

Participants will be taking concomitant AED, perhaps 1-4 AEDs. In addition they may have a VNS device inserted or be on the ketogenic diet. We require that their current regime is stable prior to initiation – 4 weeks for AED and 3 months for VNS and ketogenic diet. All concomitant anti-epileptic treatments are to be continued during the intervention period. Participants who are currently taking AEDs where trough levels can

routinely be assessed, will have levels assessed at interval throughout the study intervention period (as per the detailed schedule) to ensure safety.

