## **8. Statistics**

### **8.1 Statistical Method**

This is an observational study. The primary aims of this study are to determine the tolerability of the study treatment in a cohort of children with medication resistant epilepsy due to Dravet syndrome. As such, there are no formal statistical methods required, rather descriptive statistics will be presented to quantify dosing tolerability and frequency of adverse events. All participants will be analyzed regardless of dose achieved or duration of study completed, according to intention to treat analysis. The study data will be entered into the REDCap database for analysis.

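### Symptomatic adverse events have no scheduled pre-dose measurement, so their on-treatment frequency cannot be set against the same child's 4 weeks on background AEDs alone

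*Combined protocol and SAP*

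**What the plan says.** - **Reporting window.** Section 7.1: "The adverse event reporting period is from the initiation of the study treatment until the end of study treatment follow-up". Section 7.2 likewise places AE screening by direct questioning in the intervention period and follow-up.
- **Definition.** Section 7.1 defines an AE as "any symptom, sign, illness or experience that develops or worsens in severity during the course of the study". No reference severity is given for judging that something has worsened.
- **Run-in.** Section 3.1 provides a pre-intervention period: "This period is the first four weeks after the patient is enrolled". Sections 5.5, 5.6 and 5.8 list what is collected before the first dose. The diary covers seizures, status epilepticus, rescue medication and ER visits or hospitalisations. There are also a 24-hour EEG, the Vineland, physical and neurological examination, weight, the QOLCE, blood count, liver and renal tests, and AED troughs. No inquiry about side effects or symptoms is listed.
- **PESQ.** Section 7.2 asks for it at every clinic visit, which could be read to include Week 0. The visit descriptions in 5.6 and the schedule in 5.8 show it first at Week 2.
- **Design.** The Study Summary gives the methodology as "Open-label Intervention" with no reference therapy. Section 5.3 says: "Participants will be taking concomitant AED, perhaps 1-4 AEDs".
- **Analysis.** Section 8.1: "descriptive statistics will be presented to quantify dosing tolerability and frequency of adverse events". The Study Summary adds that AEs are to be described by dose.

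**The concern.** Starting AE collection at the first dose is defensible when a control arm supplies the background rate. This trial has no such arm. Section 1.2 introduces its list of expected effects with "The following are the most common side effects of AEDs and/or high-THC cannabis". That list includes dizziness, somnolence, fatigue, irritability, ataxia, anorexia and behavioural reactions. The protocol expects these to be minor or rare with the product because its THC content is low. That expectation cannot be examined without knowing how common the symptoms were before dosing.

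The planned table by dose does not fill the gap. Dose rises with time during titration, so the two are confounded, and the lowest dose described is the starting dose. The run-in could supply the missing zero-dose row, but the plan does not collect symptoms in it. Once dosing has begun, that information cannot be reliably recovered.

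**Working it through.** The documents give no background AE rate and no sample size calculation (8.2), so there is no stated figure to reproduce. The rates and risks below are assumptions, shown over a range.

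**1. Exposure.** Inputs: 20 children (8.2), a 4-week run-in (3.1) and 20 weeks of intervention (3.2), all completing.
- Run-in: 20 × 4 = 80 patient-weeks.
- On treatment to Week 20: 20 × 20 = 400 patient-weeks.
- Under the 5.8 titration, the seven doses from 2 to 14 mg/kg/day last one week each, or 20 × 1 = 20 patient-weeks per row. The top dose runs from Week 7 to Week 20, or 20 × 13 = 260. Check: 7 × 20 + 260 = 400. A zero-dose row of 80 patient-weeks would be four times the size of any titration row.

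**2. Events expected with no product effect.** Events = rate × patient-weeks.

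| Assumed rate per patient-week | Run-in (80) | On treatment (400) |
|---|---|---|
| 0.05 | 4 | 20 |
| 0.10 | 8 | 40 |
| 0.25 | 20 | 100 |

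**3. Precision of the comparison.** For independent Poisson counts, SE of the log rate ratio = √(1/a + 1/b).
- All events, 8 versus 40: √(1/8 + 1/40) = 0.387; exp(1.96 × 0.387) ≈ 2.1. An observed ratio of 1 has a 95% interval of about 0.47 to 2.1.
- One event type, 2 versus 10: √(1/2 + 1/10) = 0.77; interval about 0.22 to 4.6.
- Events cluster within children, so the true intervals are wider.

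**4. The same question for one symptom, per child.** Let p be the background risk over 4 weeks, constant and independent between periods. The chance of at least one event in 20 weeks is 1 − (1 − p)^5. The cited open-label study reported somnolence in 25% (1.5), which is 5 of 20 here.

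| Assumed p | Risk over 20 weeks | Expected of 20 | P(5 or more of 20) |
|---|---|---|---|
| 5% | 23% | 4.5 | 49% |
| 10% | 41% | 8.2 | 96% |
| 20% | 67% | 13.4 | above 99% |

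On these assumptions, background alone could readily produce 5 of 20. An observed 5 of 20 has a Clopper-Pearson 95% interval of 8.7% to 49.1%.

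**5. What a matched comparison could detect.** Two equal 4-week windows, 20 pairs, exact two-sided McNemar test at 0.05, responses independent within child. Power is 20% for 5% versus 25%, 10% for 10% versus 25%, 86% for 5% versus 50%, and 69% for 10% versus 50%. Only large shifts would stand out.

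**6. Ascertainment.** On treatment to Week 18 there are five clinic visits (Weeks 2, 4, 8, 12, 16) and eight calls or emails (Weeks 1, 3, 5, 6, 7, 10, 14, 18), so 13 contacts. A single question at Week 0 about the past 4 weeks is not the same intensity of inquiry.

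**The case against.** The strongest reply is that the run-in is well used. A reader might infer from 7.1 that the trial discards its only comparator. It does not. The diary outcomes, EEG, laboratory tests, AED troughs, weight, examination and QOLCE all have pre-dose values, and section 2 names blood work and AED levels as measures of the primary safety objective. The gap is confined to symptoms and the PESQ.

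Three other strong readings also fail:
- **That the protocol admits this problem in 1.7.1 and repeats it.** That section says of the cited study that "it is difficult to ascertain whether this was related to therapy or in keeping with their inherent risk of status epilepticus". The remark concerns status epilepticus only, and here status epilepticus has a diary baseline.
- **That every complaint after Week 0 counts against the product, so AE frequency overstates its effect.** An AE must develop or worsen, so a stable pre-existing AED effect is not one. Section 7.5 provides for deciding that participation was not causative. No section presents AE frequency as an increment over background; it misleads only if read that way.
- **That 7.1 contradicts itself.** A definition followed by a narrower reporting window is not a contradiction. What is missing is the reference severity for worsening.

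Two practical points stand. With 13 contacts against one recall, run-in events would probably be under-counted, which would push a raw rate ratio against the product. AEDs may also be adjusted on treatment (1.5, 1.7.1), so the background is not strictly constant. The primary endpoint is the maximal safely tolerated dose (3.4), and AE frequency supports it. These points limit how the comparison may be presented; they do not remove the value of pre-dose symptom data.

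**Conclusion.** The point holds for symptomatic adverse events and the PESQ, and no further. As written, the plan will report how often such symptoms occurred on treatment in children taking other drugs that may cause them, with no record of the same symptoms in the preceding 4 weeks. At the assumed 0.1 events per patient-week, about 40 on-treatment events would need no product effect to explain them, and the run-in would have shown about 8.

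The reference would be coarse: a factor of about 2.1 overall before clustering, and about 4.6 for a single event type. It rests on assumed rates, full follow-up and independent events. It would be unblinded, ordered in time and unequally ascertained, so it supports description and not a test. It is worth having because it costs little and cannot be reliably rebuilt after dosing. The gap does not invalidate the primary endpoint.

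**What to change.** **Section 7.1.** Record AEs and symptoms, with severity, from enrolment at Week -4. Repeat the same direct questioning at Week 0 before the first dose, together with the PESQ. Name the pre-dose severity as the reference for worsening, and count as treatment-emergent only events that start or worsen after the first dose. Leave expedited reporting of drug reactions as it is.

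**Sections 5.6, 5.8 and 7.2.** Reconcile the PESQ timing so that the visit list and the schedule show it before dosing at Week 0.

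**Section 8.1.** Add a pre-dose (zero-dose) row to the description of AEs by dose, as events per patient-week, because the windows differ in length. Call the comparison like-for-like only where ascertainment matches, for example PESQ or clinic-visit symptom prevalence at Week 0 against later clinic visits. State that it is descriptive, unblinded, time-ordered and imprecise, with 80 against 400 patient-weeks if all complete.

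**Cost.** A few sentences, one table row, and an AE form and PESQ at an existing visit. No new visit, test or staff. The downsides are slightly more data entry and possible under-recall in the run-in.
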